3. OBJECTIVES

Objectives:

Primary objective:

Assessment of arthralgia scores and patients` compliance within the first year of anastrozole treatment¹, stratified by upfront and switch therapy as well as assessment of the relationship between compliance and arthralgia scores.

Secondary objectives

Incidence of arthralgias and arthralgia characteristics within the first year of anastrozole therapy¹ stratified by upfront and switch therapy and assessment of the relationship of arthralgia incidence and arthralgia characteristics to patients` compliance.

Retrospective assessment of incidence of pre-existing arthralgias before start of anastrozole treatment, stratified by upfront and switch therapy.

Descriptive assessment of arthralgia therapy and of costs of arthralgia therapy, stratified by upfront and switch therapy.

The assessment of compliance and of arthralgia therapy will be compared to and validated by the corresponding data obtained by the sick funds of the patients.²

Assessment of subjective perception of side-effects by the patients, stratified by upfront and switch therapy.

Identification of factors influencing and correlating to treatment-emergent arthralgias, such as patient's characteristics (e.g. age, BMI), disease characteristics, duration of anastrozole treatment, subjective perception of side-effects by the patients etc.

Identification of factors influencing and correlating to patients' compliance; for example patient's characteristics (age), disease characteristics, concomitant medication, subjective perception of side-effects by the patients, incidence and characteristics of arthralgias (time between start of anastrozole therapy and occurrence, intensity and duration of arthralgias), incidence of AEs etc.

Compare time to progression (TTP) between patients with arthralgias and patients without arthralgias in the first year of anastrozole treatment, stratified by upfront and switch therapy.

Assessment of safety and tolerability of anastrozole.

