	3 – approximately half	[40% ; 60%]
	4 – more than half	[60% ; 80%]
	5 – almost all	[80% ; 100%]
	6 – all	100%.

3) A patient will only be defined as being ‘compliant’ when the answer of the doctor **and** the patient score ‘5’ or ‘6’ concerning the question regarding the number of tablets actually taken.

Upon receipt of sick fund data, for patients insured in the GWQ and who consented to data exchange, compliance data obtained in this NIS will be compared to the percentage of prescriptions actually received by the pharmacies.

Arthralgias

Arthralgias will be summarized by incidence, localization, onset, duration, intensity, and relationship to study drug, diagnostics and arthralgia management (e.g. medication, physiotherapy, doctor’s visits, change of life style etc.). Arthralgia characteristics will be particularly assessed using VAS scores (Appendices E and F).

Perception of side-effects

Subjective perception of side-effects will be evaluated using the following scores: GASE-P (Generic Assessment of Side Effects, appendices E and F), SASS (Somatosensory

Amplification Scale, appendices E and F), and BMQ (Beliefs about medicines questionnaire, appendices E and F).

Arthralgia therapy and related costs

Arthralgia therapy will be documented in the eCRF and in the patient questionnaire (for further information, see Chapter 8; e.g., newly prescribed medication, doctor's visits, diagnostics, hospital admissions). Diagnostic and therapeutic measures will be recorded as standardised patterns in the eCRF and in the patient questionnaire and will be correlated with itemised costs for evaluation purposes. Cost evaluations will be feasible on patient and global level.

Validation of data (arthralgia therapy and compliance) by sick fund data

For patients who signed an additional informed consent form (Appendix C, see chapter 7.3), arthralgia therapy as documented by the investigators and the patients will be compared to sick fund data on an individual patient level by a third party who will combine the study and the sick fund datasets on an individual patient level. The third party will combine the sick fund dataset and the study dataset using the patient insurance number which will be sent to on the additional informed consent (Appendix C). The patient insurance number will be immediately deleted after data combination. Statistical evaluation will only be based on pseudonymised data.

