11.2 Description of outcome variables

The co-primary objective of this NIS will be the evaluation of arthralgia scores and patients’ compliance. Secondary, arthralgia management and related costs (health economic evaluation) as well as the perception of side-effects will be evaluated. Data concerning arthralgia management will be compared to and validated by data obtained by the GWQ.

Compliance:

Compliance is defined by the percentage number of patients being ‘compliant’ to anastrozole therapy, based on the following information collected by the doctor at 0, 3, 6 and 9 months after study start:

1) Question about the daily intake of anastrozole (to be answered by the investigator):

”The patient was instructed to take 1 anastrozole tablet per day. However, it’s still possible that the intake has sometimes been forgotten. How many tablets, according to your impression of the patient, has the patient actually taken during the last year?”

Scoring:	0 – none	0%
	1 – few	[0% ; 20%]
	2 – less than half	[20% ; 40%]
	3 – approximately half	[40% ; 60%]
	4 – more than half	[60% ; 80%]

5 – almost all	[80% ; 100%]
6 – all	100%.

- 2) Question about the daily intake of anastrozole (to be answered by the patient in the patient questionnaire)
”You were instructed to take 1 anastrozole tablet per day. However, it’s still possible that the intake has sometimes been forgotten. How many tablets have you actually taken during the last year?”

Scoring: 0 – none	0%
1 – few	[0% ; 20%]
2 – less than half	[20% ; 40%]
3 – approximately half	[40% ; 60%]
4 – more than half	[60% ; 80%]
5 – almost all	[80% ; 100%]
6 – all	100%.

- 3) A patient will only be defined as being ‘compliant’ when the answer of the doctor **and** the patient score ‘5’ or ‘6’ concerning the question regarding the number of tablets actually taken.

Arthralgias

Arthralgias will be characterized by VAS scores containing 14 items.

Arthralgias will be summarized by incidence, localization, onset, duration, intensity, and relationship to study drug, diagnostics and arthralgia management (e.g. medication, physiotherapy, doctor’s visits, change of life style etc.). Arthralgia characteristics will be particularly assessed using VAS scores (Appendices E and F).

Perception of side-effects

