Subjective perception of side-effects will be evaluated using the following scores: GASE-P (Generic Assessment of Side Effects, appendices E and F), SASS (Somatosensory Amplification Scale, appendices E and F), and BMQ (Beliefs about medicines questionnaire, appendices E and F).

Arthralgia therapy and related costs

Arthralgia therapy will be documented in the eCRF and in the patient questionnaire (for further information, see Chapter 8; e.g., newly prescribed medication, doctor’s visits, diagnostics, hospital admissions). Diagnostic and therapeutic measures will be recorded as standardised patterns in the eCRF and in the patient questionnaire and will be correlated with itemised costs for evaluation purposes. Cost evaluations will be feasible on patient and global level.

Each occurrence of arthralgia will be assigned to the corresponding time interval according to 0-3, 3-6, 6-9, 9-12 and 12+ months after the start of anastrozole treatment (i.e. post treatment start).

Validation of data (arthralgia therapy and compliance) by sick fund data

For patients who signed an additional informed consent form (Appendix C, see chapter 7.3), arthralgia therapy as documented by the investigators and the patients will be compared to sick fund data on an individual patient level by a third party who will combine the study and the sick fund datasets on an individual patient level. The third party will combine the sick fund dataset and the study dataset using the patient insurance number which will be sent to on the additional informed consent (Appendix C). The patient insurance number will be immediately deleted after data combination. Statistical evaluation will only be based on pseudonymised data.

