11.4 Method of statistical analysis

In this section, only the important statistical aspects of the statistical analysis of the outcome variables and the adverse events are presented. Details regarding the analysis will be presented in the SAP.

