The assessment of compliance and of arthralgia therapy will be compared to and validated by the corresponding data obtained by the sick funds of the patients.²

For the subgroup of patients who consented to the data transfer of her sick funds data related to compliance and arthralgia therapy will be analyzed for correlation to the transferred data and described descriptively with standard statistics.

Assessment of subjective perception of side-effects by the patients, stratified by upfront and switch therapy.

Scores of GASE-P and SASS will be evaluated by presenting number and percentage of each category stratified by upfront and switch therapy. Groups will be compared using chi-square test.

Identification of factors influencing and correlating to treatment-emergent arthralgias, such as patient's characteristics (e.g. age, BMI), disease characteristics, duration of anastrozole treatment, subjective perception of side-effects by the patients etc.

Patient characteristics, disease characteristics and duration of anastrozole treatment will be described descriptively stratified by the occurrence of treatment-emergent arthralgias. A possible influence will be analyzed using logistic regression.

Identification of factors influencing and correlating to patients' compliance; for example patient's characteristics (age), disease characteristics, concomitant medication, subjective perception of side-effects by the patients, incidence and characteristics of arthralgias (time between start of anastrozole therapy and occurrence, intensity and duration of arthralgias), incidence of AEs etc.

Evaluation will be performed in the same way as described for the previous criterion.

Compare time to progression (TTP) between patients with arthralgias and patients without arthralgias in the first year of anastrozole treatment, stratified by upfront and switch therapy.

Time between start of anastrozole therapy and progression of disease will be analysed using the Kaplan-Meier method comparing patients with arthralgias to patients without arthralgias and upfront therapy to switch therapy.

Assessment of safety and tolerability of anastrozole.

The safety analysis will be descriptive and comprise all documented adverse events.

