11.5 Justification of sample size

Based on previous data, it can be assumed that a patients’ compliance will decrease to approximately 50% during the first year of antihormone therapy, a difference in patients’ compliance of 6% will be judged clinically relevant. In order to recognize a statistically significant difference of 6% between two groups or between different time points 1119 patients are required per group or time point.

In the following table the sample size which is needed to detect a difference of 6% is presented with the corresponding odds ratios starting with an event rate of 44% for a standard group.

Two group continuity corrected chi-square test of equal proportions (odds ratio = 1) (equal n's, 2-sided test, $\alpha= 0.05$, Power = 80%)

Group 1 proportion, π_1		I
0,44	Proportion, π_2	0,5
	Odds ratio, $\psi = \pi_2 (1 - \pi_1) / [\pi_1 (1 - \pi_2)]$	1,273
	n per group	1119

nQuery Advisor 7.0

In a newly performed study a mean arthralgia score of 4 was found with a standard deviation of 1.86. Assuming a standard deviation (sd) of 2 and a difference of 10% between 2 groups a sample size of 394 in each group will have 80% power to detect a difference in means of - 0,4 (the difference between a Group 1 mean, μ_1 , of 4 and a Group 2 mean, μ_2 of 4,4) assuming that the common standard deviation is 2 using a two group t-test with a 0,050 two-sided significance level.

In the following table the sample size which is needed to detect a difference of 10% in the arthralgia score is shown for the t-test.

Comparison of equal means (2-sided test, $\alpha= 0.05$, Power = 80%)

	t-test
Group 1 mean, μ_1	4,000
Group 2 mean, μ_2	4,400
Difference in means, $\mu_1 - \mu_2$	-0,400
Common standard deviation, σ	2,000
Effect size, $\delta = \mu_1 - \mu_2 / \sigma$	0,200
n per group	394

nQuery Advisor 7.0

Based on previous non-interventional trials, approximately 25 to 40% of the patient documentation will not be accessible. Therefore, assuming a drop-out rate of 30%, 3212 patients will be enrolled to ensure a sufficient number of evaluable patients.

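### Correlation is the only specific comparison named for validating reported compliance and arthralgia therapy against sick-fund data, and it does not measure agreement

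*Protocol*

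**What the plan says.** The secondary objectives (Protocol section 3, repeated in 11.4.1) state that the assessment of compliance and of arthralgia therapy "will be compared to and validated by the corresponding data obtained by the sick funds". This applies to consenting patients whose sick fund has joined the contract. Under outcome variables, section 3 adds that "compliance data obtained in this NIS will be compared to the percentage of prescriptions actually received by the pharmacies". Section 11.2 says that arthralgia therapy as documented by investigators and patients "will be compared to sick fund data on an individual patient level by a third party", so linkage by patient is planned.

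The method is in 11.4.1: for the consenting subgroup, the data on compliance and arthralgia therapy "will be analyzed for correlation to the transferred data and described descriptively with standard statistics". No agreement measure is named, and no criterion for calling the reports validated.

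The measure to be validated is a classification. Under 11.2 a patient is compliant only when both the doctor and "the patient score ‘5’ or ‘6’ concerning the question regarding the number of tablets actually taken". Scores 5 and 6 cover reported intake from 80% upward. Intake is recorded in seven ordered categories, not as a percentage. Section 11.4 says of the methods generally: "Details regarding the analysis will be presented in the SAP".

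**The concern.** Validating a yes/no compliance flag against dispensing asks two things: do the sources give the same percentage compliant, and how often does one confirm the other for the same patient? A correlation coefficient answers neither. If every report were too high by the same amount, the ordering of patients, and with it the correlation, would hardly change. The same applies to therapy items: if each patient reported exactly half the visits that the fund recorded, the correlation would be 1.

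Compliance is co-primary. A high coefficient in the linked subgroup would naturally be read as support for the compliance percentage in the whole study, although that percentage could be well off.

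**Working it through.** **The plan's own figures.** The validation has no sample size, expected coefficient or threshold. The only size attached to compliance is in section 11.5, which assumes that "compliance will decrease to approximately 50% during the first year of antihormone therapy", calls a 6% difference clinically relevant and gives 1119 per group for 44% against 50%. This reproduces:

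- Uncorrected: n = [1.960·√(2·0.47·0.53) + 0.842·√(0.44·0.56 + 0.50·0.50)]² / 0.06² = 1085.0, rounded up to 1086.
- Continuity-corrected: (n/4)·[1 + √(1 + 4/(n·0.06))]² = 1118.1, rounded up to 1119.

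The 6 points are a difference between groups or time points, not a validation tolerance. They serve here only as a yardstick.

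**Assumed inputs (none is in the protocol).** Prescription coverage is normal with mean 75 or 80% and SD 15, cut to 0–100. Mean 80 gives 50% at or above 80%, in line with section 11.5. Reported intake = coverage + shift + noise, cut to 0–100; shift 0, 10 or 15 points, noise SD 0, 5 or 10. The report is then put into the protocol's seven categories. Compliant means at least 80% in either source. The joint doctor-and-patient rule is simplified to one report. There were 400,000 simulated patients per setting, so these are large-sample values.

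**Results, mean coverage 80%** (sick-fund compliant 50% throughout):

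| Noise SD | Shift | Spearman, category vs coverage | Compliant by report | Report minus fund | phi | kappa |
|---|---|---|---|---|---|---|
| 0 | 0 | 0.93 | 50% | 0 | 1.00 | 1.00 |
| 0 | 10 | 0.92 | 75% | 25 | 0.58 | 0.50 |
| 0 | 15 | 0.92 | 84% | 34 | 0.43 | 0.32 |
| 5 | 0 | 0.87 | 50% | 0 | 0.79 | 0.79 |
| 5 | 10 | 0.88 | 74% | 24 | 0.59 | 0.52 |
| 5 | 15 | 0.87 | 83% | 33 | 0.45 | 0.34 |
| 10 | 0 | 0.76 | 50% | 0 | 0.62 | 0.62 |
| 10 | 10 | 0.76 | 71% | 21 | 0.55 | 0.50 |
| 10 | 15 | 0.75 | 80% | 30 | 0.47 | 0.38 |

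With mean 75% (sick-fund compliant 37%), shifts of 10 to 15 give Spearman 0.77–0.93, a gap of 24–38 points, phi 0.44–0.59 and kappa 0.33–0.52. At fixed mean and noise, Spearman never moves by more than 0.012 between no shift and a 10- or 15-point shift.

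**Correlation on the yes/no flag.** Let p be compliant by fund and q compliant by report; phi = (P(both) − p·q) / √(p(1−p)q(1−q)). Take p = 0.50.

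- If 20% of non-compliers are reported compliant, q = 0.60 and P(both) = 0.50: phi = (0.50 − 0.30)/√(0.25·0.24) = 0.82.
- If instead 20% of compliers are reported non-compliant, q = 0.40 and P(both) = 0.40: phi = (0.40 − 0.20)/√(0.25·0.24) = 0.82.

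The bias is +10 points in the first case and −10 in the second, with the same phi. In both, observed agreement is 0.90 and chance agreement 0.50, so kappa is (0.90 − 0.50)/(1 − 0.50) = 0.80. Kappa alone therefore gives no direction either; the cross-table and the paired difference do. In the table, unbiased noise of SD 10 (phi 0.62, gap 0) and a noise-free 10-point shift (phi 0.58, gap 25) look alike on phi.

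**The case against.** The strongest reply is that the sentence has two parts. Besides correlation it promises descriptive statistics, which section 11.1 defines as numbers and percentages for categorical data and standard summaries for numerical data. Section 3 also promises a comparison with the percentage of prescriptions. Shown by source, these would read 50% against 71 to 84% in the table and the bias would be plain. This stands in part: a reader might infer that the validation rests on correlation alone, and the text does not support that. But the protocol does not commit to a by-source display in the linked patients, and separate summaries cannot show patient-level agreement.

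A reader might also infer that correlation cannot detect over-reporting at all. That is too strong: on the yes/no flag phi does fall, to 0.43–0.59. Coefficients of 0.97 to 0.99 can be produced, but only for a continuous, noise-free reported percentage, which the study does not collect.

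Nor does the protocol establish that doctors and patients overstate intake, or that dispensing is the truth. It records anastrozole sample packages (8.1.3, 8.2.1), which may be absent from sick-fund data, so a gap between sources need not be over-reporting.

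Finally, details are left to the SAP, which is not shown and may name agreement measures. Their absence from the protocol is not the point. The point is that the protocol fixes correlation as its named method for validation, and an SAP following it literally would inherit the weakness.

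**Conclusion.** The point holds in limited form. Correlation is the only specific comparative method tied to the validation, and it measures association, not agreement. Under the stated assumptions, a 10 to 15 point overstatement leaves Spearman essentially where it was (0.75–0.93), while the two sources differ by 21 to 38 points in percentage compliant, at least three times the protocol's 6-point yardstick (21/6 = 3.5). Phi falls but gives neither direction nor size.

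The sizes depend on the assumed coverage distribution, noise and shift. That agreement and correlation are different things does not depend on them.

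The weight is moderate. This is a secondary objective in a consenting subgroup, p-values are exploratory (11.1), no decision rule depends on it, and the co-primary analysis itself is unchanged. A reader might infer that the compliance results are biased; nothing in the protocol shows that. What is at risk is how far the validation can support them.

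**What to change.** In 11.4.1, and correspondingly in the SAP, for the linked patients:

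- Cross-tabulate compliant yes/no by report against a pre-specified prescription-coverage cut-off, for example at least 80% to match scores 5 and 6, over the period that the question covers.
- Give the percentage compliant by each source, the paired difference with 95% CI, kappa, and positive and negative agreement. Sensitivity and specificity may be used instead of the last two if dispensing is named as an imperfect reference.
- State how recorded sample packages enter the coverage figure.
- Show prescription coverage by reported intake category. Limits of agreement are unsuitable because intake is reported only in bands.
- For each arthralgia-therapy item, give percent agreement and kappa.
- Keep correlation as a supplement.

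The cost is wording and a little more analysis on data already to be linked, with no additional patients or data items. The one new decision is the coverage cut-off, which must be fixed before the linked data are seen.

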All statistical tests will be performed two-sided at a 5% level of significance. However, the p-values of all statistical tests will be interpreted only in a descriptive-exploratory way. Two-sided confidence intervals will be displayed for important variables. Appropriate methods will be used to derive confidence intervals, depending on data nature and distribution. All safety and tolerability data (excluding data obtained on arthralgias) will be presented in a purely descriptive manner. Data from patients, who stopped anastrozole treatment and continued adjuvant endocrine treatment with a different medication will be presented in descriptive way only.

All statistical analyses will be performed using the SAS[®] system.

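### The chi-square comparison of GASE-P and SASS ignores the order of the scores and can lose power against a shift, by an amount the protocol does not let one fix

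*Protocol*

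**What the plan says.** Protocol section 11.2 introduces three instruments for this objective, GASE-P, SASS and BMQ, and calls them scores: "Subjective perception of side-effects will be evaluated using the following scores". Section 11.4.1 then sets the analysis for two of them: "Scores of GASE-P and SASS will be evaluated by presenting number and percentage of each category stratified by upfront and switch therapy". The next sentence names the test: "Groups will be compared using chi-square test". No trend, rank or mean comparison is mentioned, and BMQ does not appear in that analysis.

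The same section handles the arthralgia VAS differently. Its 14 items are averaged into an overall score and the groups are compared by t-test.

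Three statements frame the importance of the comparison. Section 11.1 says "All statistical tests will be performed two-sided at a 5% level of significance" and continues "However, the p-values of all statistical tests will be interpreted only in a descriptive-exploratory way". Section 11.2 lists perception of side-effects among the secondary evaluations. Section 11.4 adds "Details regarding the analysis will be presented in the SAP".

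**The concern.** A Pearson chi-square test on a 2 × k table gives the same result if the k categories are shuffled. It spreads its sensitivity over k − 1 degrees of freedom, whereas a shift of one group towards more perceived side-effects is a one-degree-of-freedom alternative. The more categories are tabulated, the more is lost against such a shift.

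The test also has no natural effect estimate: with more than two categories there is no single difference to carry a confidence interval. That matters in a study whose p-values are meant only to describe, and whose section 11.1 promises two-sided intervals for important variables. The protocol gives no reason for treating these questionnaire scores differently from the VAS score.

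At stake is whether a modest difference in perceived side-effects between upfront and switch patients would be seen and could be expressed as one number.

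**Working it through.** **Inputs from the protocol.** Two-sided α = 0.05 (section 11.1). Compliance 44% against 50%, 80% power, 1119 per group; arthralgia score difference 0.4 with SD 2, 80% power, 394 per group; 30% drop-out and 3212 enrolled (section 11.5).

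**Not in the protocol, so assumed.** The number of GASE-P and SASS categories (3 to 40, equally likely in the reference group), the effect (a normal shift of 0.12 or 0.20 SD) and the upfront/switch split (equal, or 80:20). The 0.20 is borrowed from the arthralgia score, 0.4/2, the only standardised mean difference the protocol plans for.

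**Step 1: the plan's own figures.**
- Compliance without correction: n′ = [1.960·√(2·0.47·0.53) + 0.842·√(0.44·0.56 + 0.50·0.50)]² / 0.06² ≈ 1085.02, so 1086. With continuity correction: (n′/4)·[1 + √(1 + 4/(n′·0.06))]² ≈ 1118.1, so 1119, as stated ("1119 patients are required per group or time point").
- Arthralgia score: 2·(1.960 + 0.842)²·2²/0.4² gives 393 by the normal approximation; the t distribution gives 393.4, so 394, as stated.
- Enrolment: 2·1119/0.70 = 3197.1, so 3198, against 3212 stated (0.4% apart).
- Evaluable: 3212·0.70 = 2248.4, or about 1124 per group if the groups are equal.

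None of these figures was derived for GASE-P or SASS.

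**Step 2: same evidence, different degrees of freedom.** A 1-df test with 80% power has non-centrality λ = (1.960 + 0.842)² = 7.849. The power of the unordered test at that λ is P[χ²(k−1, λ) > 95% point of χ²(k−1)].

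| Categories | df | Chi-square power | Sample-size factor to regain 80% |
|---|---|---|---|
| 3 | 2 | 70.9% | 1.23 |
| 4 | 3 | 64.5% | 1.39 |
| 5 | 4 | 59.5% | 1.52 |
| 10 | 9 | 44.6% | 1.99 |
| 40 | 39 | 22.0% | 3.48 |

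At 1124 per group this λ corresponds to a shift of √(2·7.849/1124) ≈ 0.12 SD.

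**Step 3: at the planned evaluable numbers.** For category probabilities p₁ⱼ and p₂ⱼ with pooled p̄ⱼ, the Pearson non-centrality is Σ_g n_g Σⱼ (p_gⱼ − p̄ⱼ)²/p̄ⱼ. For the ordered test it is (difference in mean ridit)² / [V·(1/n₁ + 1/n₂)], with V the pooled ridit variance. Entries are power, chi-square / ordered.

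| Categories | 0.12 SD, 1124 + 1124 | 0.20 SD, 1124 + 1124 | 0.20 SD, 1799 + 449 |
|---|---|---|---|
| 3 | 61.4 / 71.6% | 97.2 / 98.8% | 86.2 / 91.9% |
| 4 | 58.6 / 74.8% | 96.9 / 99.2% | 84.9 / 93.7% |
| 5 | 55.6 / 76.3% | 96.4 / 99.4% | 83.1 / 94.5% |
| 10 | 43.9 / 78.5% | 92.4 / 99.5% | 73.4 / 95.5% |
| 40 | 22.4 / 79.2% | 67.6 / 99.6% | 42.8 / 95.8% |

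At 0.20 SD and an equal split the loss is 2.3 points with 4 categories, 3.0 with 5, 7.1 with 10 and 32.0 with 40. With the 80:20 split it becomes 8.8, 11.4, 22.1 and 53.0 points. At 0.12 SD the uneven split lowers both powers but leaves the gap about the same (4 categories: 39.5% against 55.6%).

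**Step 4: simulation.** 1500 runs with the Wilcoxon test as the ordered comparison, 1124 per group and 0.12 SD gave 61% against 76% (4 categories), 46% against 80% (10) and 23% against 80% (40), in line with the formulas.

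**The case against.** The strongest reply is that the protocol states nothing false. Chi-square is a valid test of equal distributions and also picks up non-monotone differences. The objective as worded names no direction and no location shift. The comparison is secondary, its p-value exploratory, and how the scores are formed and grouped may be set in an SAP that is not at hand. All of this stands, and it keeps the point minor. It does not remove it, because the protocol itself has chosen the test, and an SAP that follows the text inherits the choice.

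Three stronger readings are tempting and are not supported.

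- A reader might infer that much of the power is wasted. That needs many categories or a small effect. The questionnaires are in appendices not shown, and a table by category fits single items with few levels as well as total scores. With 4 or 5 categories, 0.2 SD and equal groups, almost nothing is lost.
- A reader might infer that a significant result would leave the direction unknown. The percentages for each group, required in the preceding sentence of section 11.4.1, would show it. What is missing is a single difference with an interval.
- A reader might infer that BMQ will go unanalysed. Sections 8.2.1 and 8.2.2 collect it and section 11.2 names it, while the analysis paragraph omits it. The SAP may supply the analysis, so this is a side point.

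**Conclusion.** The point holds in a limited form. The specified test ignores the order of the scores and can lose power against a shift. How much is lost cannot be settled from the protocol: from 2 to 3 points (4 or 5 categories, 0.2 SD, equal groups of about 1124) to more than 50 points (40 categories with 0.12 SD, or with an 80:20 split at 0.2 SD). These figures rest on an assumed normal shift, equally likely categories and the 30% drop-out of section 11.5.

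No type I error is inflated, and no primary conclusion or sample size depends on this comparison. It is a worthwhile improvement of low severity, and the lack of a single difference with an interval holds for any table with more than two categories.

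**What to change.** In section 11.4.1, and in the SAP, replace the chi-square sentence with three rules:

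- Compare total GASE-P and SASS scores between upfront and switch by a Wilcoxon rank-sum test, or by a t-test as already planned for the VAS, and report the difference with its 95% CI.
- Use a trend test for single ordinal items.
- Keep the category percentages as description.

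Apply the same comparison to BMQ, so that the analysis covers all three scores named in section 11.2.

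The cost is about one sentence in each document, with no new data and no change to the sample size or primary analysis. The small downside is less sensitivity to non-monotone differences, which the tabulated percentages would still show.
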